6.4.5 Dose Modification Criteria (Pembrolizumab) including Immune Related AEs

Any dose modifications for pembrolizumab-related toxicity in patients enrolled on the Phase 1a Safety Lead-in will be considered a DLT and the patient will need to be replaced.

Dose modifications for pembrolizumab in the Phase 1b dose expansion will be allowed in accordance with the Keytruda® USPI. Dose reductions for pembrolizumab are not permitted. AEs associated with pembrolizumab exposure may represent an immunologic etiology. These irAEs may occur shortly after the first dose or several months after the last dose of pembrolizumab treatment and may affect more than one body system simultaneously. irAEs may be managed with interruptions of pembrolizumab, administration of corticosteroids and/or other supportive care. Dose modification and toxicity management for irAEs associated with pembrolizumab should be done in accordance with the guidelines provided in the Keytruda® USPI.

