4.1.2.2.2 FPA150 Combined with Pembrolizumab (Safety Lead-in)

Additional DLT Considerations for the Combination of FPA150 and Pembrolizumab

Because pembrolizumab is a known immune checkpoint inhibitor and one of the proposed mechanisms of action of FPA150 is immune checkpoint blockade, immune-related adverse events (irAEs) are anticipated with this combination. An irAE is defined as a clinically significant AE that is associated with study drug exposure, of unknown etiology, and is consistent with an immune-mediated mechanism. Based on that background, the first occurrence of the following irAEs will not be considered a DLT because they are expected with immune therapy:

- Grade 3 tumor flare (defined as local pain, irritation, or rash localized at sites of known or suspected tumor)
- Grade 3 rash
- Grade 3 immune-related adverse event (irAE) that resolved to a Grade 1 or less within 14 days
- Transient (resolving within 6 hours of onset) Grade 3 infusion-related AE

A second occurrence of these events (except Grade 3 tumor flare) either in the same or different patient during the DLT period will be considered a DLT

4.1.2.3 Dose-Limiting Toxicity Evaluation and Dose Escalation (FPA150 Monotherapy and Combination Safety Lead-in)

The DLT evaluation interval begins on the first day of treatment upon start of infusion and continues for 21 days. In Phase 1a Dose Escalation, patients' second dose must be at least 21 days after the first dose.

Review of safety, PK and pharmacodynamic profiles may inform decisions to add cohorts with alternative dose levels or dose regimens (eg, different dosing frequency, higher dose levels) in order to reach an optimal target exposure.

All dose escalation decisions will be based on the assessment of DLTs and overall safety and tolerability, and will be made after the last patient enrolled in each cohort has completed the first treatment cycle (ie, 21 days). Dose escalation decisions will be agreed upon by the CRC as outlined in Section [4.1.1](#).

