Patients who receive at least one dose of study drug during the 21-day evaluation interval, or patients who discontinue study treatment for drug-related AEs before the DLT evaluation interval is complete, will be considered evaluable for DLT determination. Patients who discontinue study treatment for reasons other than drug-related AEs before the DLT evaluation interval is complete may be replaced. In consultation with Investigators, the Sponsor may open cohorts at dose levels between the dose levels proposed in the protocol.

For monotherapy dose escalation an accelerated titration design enrolling at least 1 patient at each dose level is planned for dose levels 0.01, 0.03, 0.1, and 0.3 mg/kg. Dose escalation to the next dose level may proceed after at least 1 patient completes the 21-day evaluation interval. If a single patient experiences a DLT or at least 2 patients experience moderate AEs (at any dose level) during the 21-day evaluation interval, additional patients will be enrolled at the current dose level and standard 3+3 dose escalation criteria will apply for that cohort as well as all subsequent dosing cohorts. Moderate AEs are defined as \geq Grade 2 AEs regardless of attribution (except for those events clearly due to the underlying disease or extraneous causes). Grade 2 laboratory values will not be considered as moderate AEs for this purpose unless accompanied by clinical sequelae.

The algorithm outlined in Table 5 will be used for all standard 3+3 dose escalation decisions in Phase 1a monotherapy. If not already applied at a lower dose level for the reasons stated above, escalation for dose levels \geq 1 mg/kg will follow standard 3+3 dose escalation criteria.

Table 5: Phase 1a Algorithm for FPA150 Monotherapy Dose-Escalation Decisions

Number of Patients with DLT at a Given Dose Level	Dose Escalation Decision Rule
0/3	Enroll 3 patients at next dose level (next/higher cohort)
1/3	Enroll 3 additional patients at current dose level (current cohort)
$\geq 2/3$	Stop enrollment. Enter 3 more patients at the previous dose level (previous/lower cohort), if only 3 were previously entered, or at an intermediate dose level
1/6	Enroll 3 patients at next dose level (next/higher cohort)
$\geq 2/6$	Stop enrollment. Enter 3 more patients at the lower dose level (previous/lower cohort), if only 3 were previously entered, or at an intermediate dose level

Abbreviations: DLT = dose-limiting toxicity.

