6.4.4 Dose Modification Criteria for FPA150

Dose reductions for FPA150 may be permitted for patients on treatment beyond the DLT Period and can be assessed using local laboratories. If a patient requires a dose reduction of FPA150 during the DLT period, they will be considered to have a DLT and be permanently discontinued from FPA150. Dose reductions for FPA150-related AEs should follow the guidelines outlined in [Table 10](#). The treating physician may choose to interrupt or discontinue FPA150 at any time outside of these guidelines if they believe it is necessary to ensure patient safety. It is recommended that the treating physician discuss the proposed dosing modification with the FivePrime medical monitor prior to making the change. Patients may resume FPA150 if the event returns to baseline or \leq Grade 1 in accordance with the guidelines outlined in [Table 10](#). Any variations from these guidelines must be discussed with the FivePrime Medical Monitor prior to dosing and must take into consideration the overall benefit and risks for the patient of continued participation in the study.

Table 10: Dose Modification Guidelines for FPA150 (Non-infusion Toxicity)

FPA150-related Toxicity Grade	Dose Schedule	New FPA150 Dose
Grade 1 or 2	No delay or missed dose required	100% of dose
Grade 3 (first occurrence)	Delay or miss dose until recovery to baseline or Grade 1	If recovery to baseline or Grade 1 within 28 days, may resume at 100% of starting dose or 1 dose lower ^a
Grade 3 (second occurrence)	Delay or miss dose until recovery to baseline or Grade 1	If recovery to baseline or Grade 1 within 28 days, may resume at 1 level lower ^a than previous dose or discontinue
Grade 3 (third occurrence) Grade 3 which does not recover to baseline or Grade 1 within 28 days Any Grade 4	Permanently Discontinue	N/A

^a Eg, 1 dose level lower for patients treated at 20 mg/kg is 10 mg/kg; 1 dose level lower for patients treated at 10 mg/kg is 3 mg/kg; 1 dose level lower for patients treated at 3 mg/kg is 1 mg/kg.

There is a \pm 3-day window for the first 3 scheduled FPA150 dosing visits. The first dose of each cycle is considered Day 1 of each cycle. Cycles will repeat every 21 days unless there is a treatment delay. Inpatient dose escalation will not be permitted above 1mg/kg except as detailed in [Section 6.4.2](#). Any patient whose dose of FPA150 is decreased cannot be subsequently increased.

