Pembrolizumab: Pembrolizumab may cause severe or life threatening infusion-reactions including severe hypersensitivity or anaphylaxis. Signs and symptoms usually develop during or shortly after drug infusion and generally resolve completely within 24 hours of completion of infusion. Dose modification and toxicity management for infusion reactions associated with pembrolizumab should be in accordance with the guidelines provided in the Keytruda® USPI.

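### In the Safety Lead-in, Section 6.4.5 counts every pembrolizumab dose modification for related toxicity as a DLT and replaces the patient, contradicting the first-occurrence exemption in 4.1.2.2.2 and the DLT evaluability rules.

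*Protocol*

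**What the plan says.** **What counts as a DLT.** Section 6.4.5 states: "Any dose modifications for pembrolizumab-related toxicity in patients enrolled on the Phase 1a Safety Lead-in will be considered a DLT". It gives no grade threshold, no time window and no reference to any exemption.

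Section 4.1.2.2.2 (and the synopsis) says: "the first occurrence of the following irAEs will not be considered a DLT because they are expected with immune therapy". The list is Grade 3 tumor flare, Grade 3 rash, a Grade 3 irAE that falls to Grade 1 or less within 14 days, and a Grade 3 infusion-related event that resolves within 6 hours. A second occurrence, tumor flare apart, "either in the same or different patient during the DLT period will be considered a DLT".

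The matching rule for FPA150 in Section 6.4.4 does carry a window: "If a patient requires a dose reduction of FPA150 during the DLT period, they will be considered to have a DLT". Under Section 4.1.2.3 the DLT interval runs for 21 days from the start of the first infusion.

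**Who is replaced.** Under 6.4.5 the modification "will be considered a DLT and the patient will need to be replaced". Elsewhere:
- Section 4.1.2.3 makes anyone who received at least one dose in the interval evaluable, and adds that "patients who discontinue study treatment for drug-related AEs before the DLT evaluation interval is complete, will be considered evaluable for DLT determination". On replacement it says: "Patients who discontinue study treatment for reasons other than drug-related AEs before the DLT evaluation interval is complete may be replaced".
- Section 7.3 provides replacement in the Safety Lead-in for patients who are unevaluable for DLT.
- Protocol Section 9.2 and SAP Section 3.1.3 both place a patient with a Cycle 1 DLT in the DLT-evaluable set.

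**The concern.** Determining the MTD and/or RD of FPA150 with pembrolizumab is a primary Phase 1a objective, and cohort 1bC1 opens at the dose so chosen. That choice rests on DLT counts read against Table 6. If two sections classify the same event differently, the same patients can produce different counts and different dosing decisions. Section 6.4.5 is the stricter text, so it can trigger de-escalation where 4.1.2.2.2 would let the level continue.

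The replacement clause is a separate problem. Replacement normally restores a denominator when a patient contributes no DLT information. A patient with a DLT has contributed decisive information. Replacing that patient either yields a count that Table 6 does not cover or removes an observed DLT from the count. The SAP tabulates DLTs (Section 7.1.7) without settling either point.

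**Working it through.** The plan states no figure on this point. The check sets the rules side by side and then runs the resulting counts through Table 6.

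**Step 1. Can an exempt event lead to a pembrolizumab modification?** Sections 6.4 and 6.4.5 bar dose reductions for pembrolizumab, so a modification has to be an interruption, hold or discontinuation. Two routes follow.
- *Transient Grade 3 infusion event on Cycle 1 Day 1.* The event falls inside the 21-day interval. Section 6.4.6, on dose interruptions, sits under 6.4 Dose Modifications and refers to "Dose modification and toxicity management for infusion reactions associated with pembrolizumab". Interrupting the infusion is a modification under 6.4.5, while the event itself is exempt under 4.1.2.2.2. This is the clearest case.
- *Grade 3 rash or reversible Grade 3 irAE.* Pembrolizumab is given on Day 1 of each 21-day cycle, so the dose that would be held is due on Day 22, just after the interval ends. Because 6.4.5 has no window, the hold is still a DLT by its wording.

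**Step 2. The count under each section.** Let k be the number of the first 3 patients who have the same exempt event type (not tumor flare) within the DLT period, each with a pembrolizumab modification. Assume no other DLTs.
- Under 4.1.2.2.2 the first occurrence is excused and later ones count: DLTs = max(k − 1, 0).
- Under 6.4.5 each one counts: DLTs = k.

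| k | 4.1.2.2.2 | Table 6 decision | 6.4.5 | Table 6 decision |
|---|---|---|---|---|
| 1 | 0/3 | proceed to up to 10 | 1/3 | enrol 3 more |
| 2 | 1/3 | enrol 3 more | 2/3 | stop, de-escalate |
| 3 | 2/3 | stop, de-escalate | 3/3 | stop, de-escalate |

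The decision differs for k = 1 and k = 2.

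**Step 3. The replacement clause.** Take one DLT in the first 3 patients, arising under 6.4.5.
- *DLT patient kept, replacement added:* 3 + 1 = 4, so 1/3 becomes 1/4. After the 3 further patients called for at 1/3, the denominator is 6 + 1 = 7, giving 1/7 or, with one more DLT, 2/7. Table 6 has rows only for denominators 3 and 6.
- *DLT patient dropped:* the count returns to 3 patients with the observed DLT removed. This contradicts 4.1.2.3, Protocol 9.2 and SAP 3.1.3, all of which keep that patient evaluable.

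Neither reading gives a count that both follows the evaluability rules and can be looked up in Table 6.

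**The case against.** The strongest reply is that the rules are cumulative. Section 4.1.2.2.2 excuses events by type and grade. Section 6.4.5 adds an action-based criterion, as 6.4.4 does for FPA150, so an event loses its exemption once pembrolizumab dosing is affected. That is a coherent design, but the protocol nowhere states it and 4.1.2.2.2 is unconditional. It also leaves the replacement clause unexplained.

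Other points carry some weight:
- The window is narrow. An exempt irAE that starts by about Day 8 and resolves within 14 days is over by Day 22, so no hold may arise. The sentence in 6.4.5 about managing irAEs by interruption sits in a paragraph that opens with Phase 1b. The Day 1 infusion reaction does not depend on either fact.
- Section 6.4.6 does not say outright that an interrupted pembrolizumab infusion is a dose modification; it defers to the prescribing information. With reductions barred, and with interruptions placed under 6.4, it is the natural reading.
- Denominators other than 3 and 6 can arise without 6.4.5. At least 3 patients may be enrolled, and Section 2.2.5.3 reports four monotherapy patients at 20 mg/kg. That is a reason not to create more of them by rule.
- Section 7.3 does not say that only unevaluable patients are replaced, and the discontinuation wording in 4.1.2.3 does not strictly cover a held dose. The one-dose limb of 4.1.2.3 does cover it, and a Cycle 1 DLT is evaluable under Protocol 9.2 and SAP 3.1.3.
- The stricter rule errs toward caution, at the price of three more patients or a lower FPA150 dose. This is true of the counting rule. It does not hold for the replacement clause if the replaced patient is dropped.

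**Conclusion.** The concern holds on both halves. The same event can be a DLT under 6.4.5 and not under 4.1.2.2.2, shifting the Table 6 count by one patient and changing the decision when one or two of the first three patients are affected. The replacement clause conflicts with 4.1.2.3, 7.3, Protocol 9.2 and SAP 3.1.3.

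The two-patient comparison assumes events of the same listed type, tumor flare excluded, within the DLT period and with no other DLTs. The first half also assumes that an interrupted or held dose is a modification. The denominators 4 and 7 assume that the DLT patient stays in the count. No probability is attached, because the documents give no event rates and leave the hold triggers to the pembrolizumab prescribing information. The missing window in 6.4.5 looks like a drafting omission. The text should be corrected because it bears on a primary dose decision, although the counting error by itself is in the cautious direction.

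**What to change.** Amend Section 6.4.5 so that a pembrolizumab dose modification for related toxicity is a DLT when the toxicity has its onset during the 21-day DLT interval, unless the event is exempt under 4.1.2.2.2. Tying the rule to onset rather than to the date of the modification is deliberate, since the dose held for a Cycle 1 rash or irAE falls on Day 22.

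Delete the clause requiring the patient to be replaced. Section 4.1.2.3, Section 7.3, Protocol 9.2 and SAP 3.1.3 already keep a DLT patient as evaluable and provide for replacing the others.

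If the sponsor does intend a modification to cancel the exemption, 4.1.2.2.2 should say so; the replacement clause should go in either case. Since 6.4.5 has no grade threshold, the amendment should also confirm whether holds for lower-grade toxicity are meant to count.

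The cost is protocol wording only. Table 6, the sample size and the SAP analysis sets do not change.

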6.4.6 Dose Interruptions During Study Treatment Administration

FPA150: Infusion must be stopped if any AE \geq Grade 3 occurs during the infusion. If bronchospasm or dyspnea occurs in a patient during the infusion, the infusion must be stopped.

In addition, at the Investigator's discretion, the infusion rate for FPA150 may be reduced or stopped if a less severe AE (Grade 1 or 2) occurs during the infusion. If a Grade 3 or less severe AE resolves within 4 hours, the infusion may be restarted at half the previous rate and promptly managed according to the discretion of the Investigator. If the same AE appears again with the same severity at any time during the restarted infusion, the infusion should be discontinued, and no further dosing of FPA150 will occur without consultation with the Sponsor or Sponsor's designee.

If a patient experiences an infusion reaction prior to completion of the infusion, the infusion must be stopped, and the patient should be promptly managed and monitored according to signs and symptoms, and local clinical protocol until there is a complete resolution of the event. Symptoms of infusion reactions may include: fever, chills, rigors, urticaria, hypotension and hypertension with headache, wheeze, breathlessness, hypoxia, and pulmonary infiltrates. For patients whose infusion-associated events were either Grade 1 or 2, and completely resolved on the day of the infusion, the infusion may be resumed at the discretion of the Investigator at a slower rate with premedication. All subsequent infusions for that patient should then be administered at the reduced rate of infusion with pre-medications. Pre-medications may include medications such as corticosteroids, diphenhydramine, acetaminophen and/or bronchodilators as indicated. FPA150 will be permanently discontinued for patients who have experienced Grade 3 or above infusion-associated AEs, and for patients who have recurrent infusion-associated reactions after restarting the infusion despite pre-medications and slower infusion.

If a patient experiences an infusion reaction, the patient's vital signs (temperature, blood pressure, pulse, and respiration rate) should be monitored during the infusion, as well as every 30 minutes after the infusion for a minimum of 2 hours and until resolution of the infusion reaction.

Pembrolizumab: Pembrolizumab may cause severe or life threatening infusion-reactions including severe hypersensitivity or anaphylaxis. Signs and symptoms usually develop during or shortly after drug infusion and generally resolve completely within 24 hours of completion of infusion. Dose modification and toxicity management for infusion reactions associated with pembrolizumab should be in accordance with the guidelines provided in the Keytruda® USPI.

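### Protocol 6.4.6 gives opposite instructions for a Grade 3 infusion-associated AE that resolves within 4 hours: one paragraph permits a half-rate restart, the next requires FPA150 to be stopped for good

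*Protocol*

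**What the plan says.** The FPA150 part of Protocol 6.4.6 has three paragraphs that matter here.

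- **First paragraph.** The infusion must stop for any AE of Grade 3 or above, and for bronchospasm or dyspnea.
- **Second paragraph.** For Grade 1-2 events, slowing or stopping is left to the investigator. Then: "If a Grade 3 or less severe AE resolves within 4 hours, the infusion may be restarted at half the previous rate". If the same event reappears at the same severity, that infusion ends and "no further dosing of FPA150 will occur without consultation with the Sponsor" or its designee.
- **Third paragraph, on infusion reactions.** The infusion must stop at any grade. After a Grade 1-2 event that has completely resolved the same day, "the infusion may be resumed at the discretion of the Investigator at a slower rate with premedication", and all later infusions are also slowed and premedicated. Beyond that, "FPA150 will be permanently discontinued for patients who have experienced Grade 3 or above infusion-associated AEs", and the same applies "for patients who have recurrent infusion-associated reactions after restarting the infusion despite pre-medications and slower infusion".

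Elsewhere, Protocol 6.3.1 only refers back to 6.4.4 and 6.4.6. Table 10 in 6.4.4 is restricted by its title to non-infusion toxicity. The SAP contains no rule on the matter.

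For the combination lead-in, Protocol 4.1.2.2.2 lists events whose first occurrence is not a DLT, among them "Transient (resolving within 6 hours of onset) Grade 3 infusion-related AE". A second occurrence "either in the same or different patient during the DLT period will be considered a DLT".

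**The concern.** The restart permission in the second paragraph covers any AE up to and including Grade 3. It is not limited to events unrelated to the infusion, and the third paragraph does not say that it takes precedence. The surrounding text makes the overlap easy to fall into: bronchospasm and dyspnea appear in the first paragraph as AEs during the infusion, while wheeze and breathlessness appear in the third as symptoms of an infusion reaction.

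The main stake is patient safety. A site that reads the second paragraph at the bedside after a Grade 3 infusion reaction would restart a drug that the third paragraph says the patient must never receive again. A secondary stake is DLT counting in the combination lead-in, where a repeat event after a restart might be scored as a DLT.

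**Working it through.** No sample size, power or error rate is involved. The check sets the two rules side by side and then follows the DLT consequence.

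**Step 1. The two paragraphs compared**

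| Event during FPA150 infusion | Second paragraph | Third paragraph | Can both be met? |
|---|---|---|---|
| Grade 3 infusion-associated AE, resolved within 4 hours | Half-rate restart permitted | Permanent discontinuation | Only by not using the permission |
| Grade 1-2 infusion-associated AE | Slowing or stopping optional; half-rate restart if resolved within 4 hours; no premedication required | Stop mandatory; resume after complete same-day resolution, slower, with premedication | Yes: stop, premedicate, restart at half rate |
| Recurrence after restart | Infusion ends; no further dosing without consulting the sponsor | Permanent discontinuation if premedication and slowing have failed | Yes: a permanent stop breaches nothing in the second paragraph |

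Only the first row gives opposite outcomes. In the other two rows the requirements differ, but one course of action meets both. Consulting the sponsor is a minimum condition; it does not in itself authorise more dosing.

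**Step 2. Search for a tie-breaker.** Protocol 6.3.1, 6.4.4 with Table 10, and 4.1.2.2.2 were checked, as was the SAP. None limits the second paragraph or ranks the two. Section 4.1.2.2.2 governs DLT counting only and says nothing about restarting.

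**Step 3. Reach of the DLT consequence.** In monotherapy escalation, Protocol 4.1.2.2.1 already makes a Grade 3 non-hematologic toxicity a DLT in the first 21 days, subject to its listed exceptions, so a restart would not change whether that patient has a DLT. Dose exploration is outside formal DLT counting (4.1.3). That leaves the combination lead-in, planned at 6 to 22 patients (4.2).

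**Step 4. Route to an added DLT in the lead-in**

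- The second paragraph uses 4 hours and the DLT exemption uses 6 hours from onset. The start of the 4 hours is not stated. If it is onset (assumption), 4 < 6, so every Grade 3 infusion-related AE eligible for restart also meets the first-occurrence exemption.
- If the event reappears at Grade 3 during the restarted infusion, and if that is a second occurrence (assumption), it is a DLT.
- One added DLT then moves each non-stopping row of Protocol Table 6: 0/3 to 1/3 (proceed becomes enrol 3 more), 1/3 to 2/3 (enrol 3 more becomes de-escalate), 1/6 to 2/6 (proceed becomes de-escalate).

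One extra DLT does this in any 3+3 scheme. The step shows what would follow, not how likely it is.

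**Step 5. Frequency.** No infusion-reaction rate and no combination data are given. Protocol 2.2.5.4 reports no DLTs in the escalation cohorts, and 2.2.5.3 counts 18 escalation patients exposed, so no Cycle 1 event of this kind was counted as a DLT there. Among 24 patients there was one Grade 3 treatment-related AE, hypertension (2.2.5.5); its timing relative to infusion is not given.

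**The case against.** The strongest reply is that the two paragraphs can be read together. The second only permits; the third, immediately after it, is specific and mandatory. On ordinary principles the specific rule governs, and a site that follows it breaches nothing. On this view the defect is a missing cross-reference, and harm requires someone to overlook the adjacent paragraph. The reading of intent stands, and it limits the seriousness of the point. But the text leaves sites to infer precedence when deciding whether to restart an infusion in a first-in-human study, and the permission as worded does cover the event that the next paragraph prohibits.

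Two stronger readings are tempting and should be resisted.

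- A reader might infer that the paragraphs contradict each other at every grade and on recurrence. The comparison above shows otherwise: outside Grade 3 or above, both can be met.
- A reader might infer that the added DLT could not arise if the third paragraph were followed. The documents do not support that. Under Protocol 6.5 a patient who stops one drug may continue the other, and 4.1.2.2.2 is not limited to FPA150 infusions, so pembrolizumab could supply a second event in the same patient. A second event in a different patient counts in any case.

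**Conclusion.** The conflict is real and confined to Grade 3 infusion-associated AEs that resolve within 4 hours. It should be corrected because the consequence of the wrong choice is re-exposure of a patient for whom the Protocol requires a permanent stop. Section 6.4.6 also applies in Phase 1b, planned for up to 210 patients. The frequency is probably low but cannot be estimated from the documents.

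The DLT effect is secondary. It is confined to the combination lead-in and rests on counting a reappearance during a restarted infusion as a second occurrence, which Protocol 4.1.2.2.2 does not say.

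Two further inferences do not hold. A reader might conclude that the only reporting effect would be on the count of FPA150 discontinuations due to AEs. Disposition (SAP 4.1) and exposure (SAP 4.2) would differ for the same patient too. A reader might also link this to the DLT-evaluable definitions, since a patient stopped after one exempt event lacks the two doses required in Protocol 9.2 and SAP 3.1.3. The mismatch between those definitions and the one-dose rule in Protocol 4.1.2.3 affects any early discontinuation. It does not come from 6.4.6 and would not be cured by amending it.

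**What to change.** Add one sentence at the end of the second paragraph of Protocol 6.4.6:

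*This restart provision does not apply to infusion reactions or infusion-associated AEs of any grade, which are managed only under the following paragraph.*

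The sentence should not restate the third paragraph's rules. A summary could easily omit the same-day resolution requirement, the premedication of all later infusions or the stop on recurrence, and so create a new inconsistency. The second paragraph stays as it is for AEs that are not infusion-associated.

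The cost is one sentence of protocol wording, with no change to sample size or analyses. The possible downside is an occasional additional FPA150 discontinuation at sites that would otherwise have relied on the restart permission.
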